9.3.3.1. AE of special interest identified by PTs

The number and percentage of subjects experiencing TEAEs of special interest will be summarized for each treatment arm by type of event. The incidence rate of AE of special interest per 100 patient years will also be summarized. It will be calculated as the total number of AEs / total patient years in specific treatment arm (or total) * 100. Each category of events will be displayed in a separate listing. Summary will also be conducted for subjects who have been prescribed insulin or sulfonylurea to control their diabetes

9.3.3.2. Hypoglycemic Events

Hypoglycemic event categories include:

Category	Description
Severe	Assistance required and blood glucose ≤ 70 mg dL ⁻¹ or no value available but responded to glucose treatment
Documented Symptomatic	Blood glucose ≤ 70 mg dL ⁻¹ and typical symptoms of hypoglycemia
Asymptomatic	Blood glucose ≤ 70 mg dL ⁻¹ and no typical symptoms of hypoglycemia

Category	Description
Probable Symptomatic	Typical symptoms of hypoglycemia and no value available but responded to glucose treatment
Relative	Typical symptoms of hypoglycemia and blood glucose >70 mg dL ⁻¹

Although each event meeting the criteria above will be entered into the hypoglycemia log, only critical (severe) hypoglycemia, documented symptomatic hypoglycemia, asymptomatic hypoglycemia, and probable hypoglycemia will be entered as AEs.

The number and percentage will be summarized by treatment for:

- Each category of hypoglycemic event;
- Severe or documented hypoglycemic events.

Summary will also be conducted for subjects who have been prescribed insulin or sulfonylurea to control their diabetes

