6.10.10 Hypoglycemia

Events of hypoglycemia or potentially representing hypoglycemia should be carefully evaluated.

All subjects will be provided with a glucometer and diary for recording blood glucose measurements and signs and symptoms that may be related to hypoglycemia, hyperglycemia, or potential diabetic ketoacidosis. During the study the subject is expected to perform daily fasting blood glucose readings and record all signs and symptoms. In the event of possible signs or symptoms of hypoglycemia, the subject is expected to check the blood glucose if it is reasonably safe to do so, and consume carbohydrates, if appropriate, to treat hypoglycemia.

The subject will be expected to record in the glycemic control diary the following information:

1. SMBG reading at the time of the signs and symptoms attributed to hypoglycemia
2. Time elapsed from the most recent food to the onset of signs and symptoms
3. Type of treatment used (e.g., juice, crackers) for the signs and symptoms and whether assistance was required from another person to administer the treatment
4. SMBG reading 15 minutes after treatment
5. Signs and symptoms attributed to hypoglycemia, hyperglycemia, or potential symptoms that may suggest ketoacidosis

Subjects will be encouraged to call the study clinic should signs and symptoms be potentially related to hypoglycemia or ketoacidosis.

At each study visit, the investigator is expected to review the glucometer recordings and glycemic control diary with particular attention to any SMBG value ≤ 70 mg/dL and any recorded signs or symptoms potentially related to hypoglycemia. In addition, the investigator should query the subject with regard to the occurrence of signs and symptoms potentially related to hypoglycemia even if none are recorded in the diary.

In the event of a blood glucose value ≤ 70 mg/dL or signs and symptoms potentially related to hypoglycemia, the investigator should complete the supplemental CRF which will include data from the glycemic control diary and action items to reduce future hypoglycemia episodes.

Hypoglycemia events will be recorded in the hypoglycemia log under 5 categories:

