1. Severe hypoglycemia: an event requiring assistance by another person to actively administer carbohydrate, glucagon, or other resuscitative actions. These episodes may be associated with sufficient neuroglycopenia to induce seizure or coma. Plasma glucose measurements may not be available during such an event, but neurological recovery attributable to the restoration of plasma glucose to normal is considered sufficient evidence that the event was induced by a low plasma glucose concentration. All such events should be recorded as SAEs in the CRF.
2. Documented symptomatic hypoglycemia: an event during which typical symptoms of hypoglycemia are accompanied by a measured plasma glucose concentration ≤ 70 mg/dL (3.9 mmol/L).

3. Asymptomatic hypoglycemia: an event not accompanied by typical symptoms of hypoglycemia but with a measured blood glucose concentration ≤ 70 mg/dL (3.9 mmol/L).
4. Probable symptomatic hypoglycemia: an event during which symptoms of hypoglycemia are not accompanied by a blood glucose determination but that is presumably caused by a blood glucose concentration ≤ 70 mg/dL (3.9 mmol/L).
5. Relative hypoglycemia: An event during which the person with diabetes reports any of the typical symptoms of hypoglycemia, and interprets those as indicative of hypoglycemia, but with a measured plasma glucose concentration > 70 mg/dL (3.9 mmol/L).

While each event meeting the criteria above will be entered into the hypoglycemia log, only severe hypoglycemia, documented symptomatic hypoglycemia, asymptomatic hypoglycemia, and probable hypoglycemia will be entered as AEs.

In the event of asymptomatic hypoglycemia, the investigator should review the signs and symptoms of hypoglycemia with the subject to elicit a complete description and should review proper glucometer technique to ensure that the low glucose value is not due to improper use of the glucometer.

The investigator should be alerted to the likelihood of improper glucose measurement technique if a study subject reports an SMBG value < 55 mg/dL (3.1 mmol/L) that is not associated with any signs or symptoms of hypoglycemia and is not treated by some form of glucose administration.

In the event of probable symptomatic hypoglycemia, the investigator should encourage the subject to obtain glucose values, when possible, in the context of signs and symptoms of hypoglycemia, even if the glucose value is measured after treatment for the symptoms is administered.

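### The SAP defines severe hypoglycemia more narrowly than the protocol and does not declare it; if categories are derived from the SAP table, some assisted events would not be counted as Severe

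*Combined protocol and SAP*

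**What the plan says.** Protocol 6.10.10 defines severe hypoglycemia as "an event requiring assistance by another person to actively administer carbohydrate, glucagon, or other resuscitative actions". It sets no glucose threshold. It adds that a glucose measurement may be lacking, and that neurological recovery once glucose is restored is then enough evidence. Every such event is to be recorded as an SAE. Sites enter events in a hypoglycemia log under five categories.

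SAP 9.3.3.2 opens its Severe category with a glucose limit, "Assistance required and blood glucose ≤ 70 mg"/dL; the full row reads "Assistance required and blood glucose ≤ 70 mg dL ⁻¹ or no value available but responded to glucose treatment". It describes the Relative category as "Typical symptoms of hypoglycemia and blood glucose >70 mg dL ⁻¹", with no exclusion for assisted events. On AE status it says that "only critical (severe) hypoglycemia, documented symptomatic hypoglycemia, asymptomatic hypoglycemia, and probable hypoglycemia will be entered as AEs"; Relative is the category left out. The planned counts are one per category plus a combined row, "Severe or documented hypoglycemic events", repeated for subjects prescribed insulin or sulfonylurea.

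The SAP's Probable Symptomatic category also requires a response to glucose treatment. The protocol's category of that name needs only symptoms without a glucose determination, presumed to be caused by low glucose.

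SAP section 12, which lists changes from the protocol's analysis, mentions none of this.

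**The concern.** Two definitions of the same safety outcome are in force, and the narrower one sits in the document that governs the tables. The difference matters most when treatment is given before glucose is measured. The protocol's diary asks for a reading when symptoms occur, but subjects are told to check only where that is reasonably safe. The diary also asks for an "SMBG reading 15 minutes after treatment". If the later reading is the only one, or is the one selected, successful treatment can put it above 70 mg/dL. The SAP never says which reading is the event's glucose value.

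Hypoglycemia is an adverse event of special interest, and protocol 9.6.1 expects about half of the randomized subjects to be on insulin. At stake is whether the Severe row and the combined row match the protocol's definition and agree with the SAE output.

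**Working it through.** There is no sample-size or power figure to reproduce. The check is to apply both sets of rules to every kind of assisted event.

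Inputs: the category definitions in protocol 6.10.10 and in the SAP 9.3.3.2 table. An assisted event is described by typical symptoms (yes or no), the event's glucose value (≤ 70 mg/dL, none, > 70 mg/dL) and documented response to glucose treatment (yes or no). That gives 2 × 3 × 2 = 12 patterns. The SAP's Severe row can be read in two ways: assistance may govern the whole row, or only its first half. The result for assisted events is the same under both.

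| Symptoms | Glucose value | Response | Patterns | Protocol | SAP |
|---|---|---|---|---|---|
| either | ≤ 70 | either | 4 | Severe | Severe |
| either | none | yes | 2 | Severe | Severe |
| either | none | no | 2 | Severe | no category |
| typical | > 70 | either | 2 | Severe (wording also fits Relative) | Relative only |
| none recorded | > 70 | either | 2 | Severe | no category |

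The table shows a second category only where it decides the outcome. All 12 patterns are Severe in the protocol; 4 + 2 = 6 are Severe in the SAP and 2 + 2 + 2 = 6 are not. These are logical patterns, not frequencies, so 6 of 12 does not mean that half of assisted events would be lost. It shows only that the SAP's Severe set lies strictly inside the protocol's.

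The patterns that leave Severe also miss the combined row, since neither Relative nor an unclassified event belongs there.

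For Probable Symptomatic, take an unassisted event with typical symptoms, no reading and no treatment, which resolves by itself. It can be Probable Symptomatic in the protocol. In the SAP it fails the response condition and fits no category.

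**The case against.** **The SAP may not re-derive anything.** The protocol has sites assign the category in the log, and SAP 9.3.3.2 gives no algorithm and no instruction to override it. If the logged category is tabulated, and sites used the protocol's definitions, no event is lost. This stands, and it makes the undercount conditional. The SAP does not say which source governs, and its printed definition would still differ from the one used.

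**The protocol also expects low glucose.** Its remark on neurological recovery, and the general definition in protocol 6.10.2 (a value ≤ 70 mg/dL), suggest that the SAP row is shorthand for the same idea. This stands only in part. The recovery remark covers missing measurements and sets no limit. The general definition cannot filter every event, because 6.10.10 itself has categories with no reading and with a reading above 70.

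**The overlap with Relative is already in the protocol.** True: the protocol's Relative category does not exclude assisted events either. There, however, the event also meets Severe; in the SAP it meets only Relative.

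**Post-treatment readings need not decide the category.** An event with an onset reading ≤ 70 mg/dL stays Severe in the SAP, provided that reading is the one used. The protocol's encouragement to measure "even if the glucose value is measured after treatment for the symptoms is administered" concerns probable symptomatic events, so it does not show that such readings are expected for severe ones. Both limits stand.

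**Removing the glucose limit goes further than needed.** Treating a post-treatment-only reading as no value already returns treated responders to Severe. Removing the limit would also count an assisted event with a pre-treatment value above 70. That is so, and it follows from the protocol's wording.

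**Conclusion.** The SAP's Severe category is narrower than the protocol's, Probable Symptomatic is narrowed too, and neither change is declared. That much rests on the text alone.

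The effect on the counts is conditional. An assisted event moves to Relative if categories are derived from the SAP table, typical symptoms were present, and the only or selected reading is a post-treatment value above 70 mg/dL. An assisted event with no value and no documented response may fit no category. The Severe and combined rows could then be undercounted, overall and in the insulin and sulfonylurea subsets. These rows are descriptive; no test in the hierarchy depends on them.

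Three stronger readings are tempting but unsupported:
- A reader might infer that the events vanish from the adverse event data because Relative is not an AE category. The protocol still makes every assisted event an SAE, so it should appear in the serious-event tables and listings of SAP 9.3.2. The risk is disagreement between outputs.
- A reader might want a number of lost events. The documents give neither a rate of assisted events nor the share with only a post-treatment reading, so any figure would be invented.
- A reader might assume that the lost events are the more serious ones. Nothing in the documents shows this.

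**What to change.** Reconcile the SAP 9.3.3.2 table with the analysis definitions in protocol 6.10.10:

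1. Define Severe by the need for another person's assistance, and remove the added response condition from Probable Symptomatic.
2. State that a reading taken only after treatment does not count as the event's glucose value.
3. State that an assisted event is counted as Severe and not as Relative, which also settles the overlap in the protocol's wording.
4. State whether the category is taken from the hypoglycemia log or derived.

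If any departure from the protocol's categories is intended, declare it in SAP section 12.

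The cost is minor SAP wording and programming. The diary already asks for assistance, treatment, the reading at symptoms and the 15-minute reading as separate items, and diary data go into the supplemental CRF. The severe count may rise slightly.

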9.3.3.3. Cardiovascular Events

The events of interest include any protocol defined MACE event of cardiovascular mortality, non-fatal MI, non-fatal stroke, transient ischemic attack, hospitalization for unstable angina, hospitalization for heart failure, and coronary revascularization. Cardiovascular events considered as any events under protocol defined MACE event by the investigator will be submitted to an independent CEC for adjudication. The number, percentage and incidence rate per 100 patient years of the adjudicated MACE will be summarized for each treatment arm. Adjudicated MACE will be further summarized by PTs. MACE will be summarized in the same table of AE of special interest.

9.3.3.4. Revascularization and Amputations

Revascularization and amputation information is collected in a separate form. Frequency and percentage will be summarized for:

- Type of procedures - cardiovascular-related or amputation
- Subjects with any amputation
- Condition that resulted in amputation
- Location of amputation

Only procedures performed after the first dose of double-blind study drug will be summarized. Summary will also be conducted for subjects who have been prescribed insulin or sulfonylurea to control their diabetes.

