9 PLANNED STATISTICAL METHODS

9.1 General Considerations

The following sections provide a summary of the planned analysis of the trial but a full analysis plan will be developed as a separate document and will become the final plan. All statistical analyses will be performed using SAS Version 9.4 or higher.

Data summaries will use descriptive statistics (number of subjects [N], mean, standard deviation [SD], Q1, median, Q3, minimum, and maximum) for continuous variables, and frequency and percentage of subjects for categorical and ordinal variables. If there are missing values, the number missing will be presented, but without a percentage.

Unless otherwise specified, all tests will be two-tailed using a 0.05 level of significance. All confidence intervals (CIs) will be two-sided 95% confidence intervals.

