9.6.4 Other Safety Endpoints

The other safety endpoints include

- Time to a 5-point composite adjudicated endpoint of CV death, non-fatal MI, non-fatal stroke, hospitalization for unstable angina, or coronary revascularization
- Time-to a 6-point composite adjudicated endpoint of CV death, non-fatal MI, non-fatal stroke, hospitalization for unstable angina, hospitalization for heart failure, and coronary revascularization; and time to onset of event
- Time to individual events including all-cause mortality, CV death, non-fatal MI, non-fatal stroke, transient ischemic attack, hospitalization for unstable angina, hospitalization for heart failure, and coronary revascularization; and time to onset of each event
- Incidence of treatment emergent AEs (TEAEs) of interest
- Incidence of amputations
- Change from baseline in eGFR by study visit
- Change from baseline in UACR by study visit

AEs of special interest include the following categories:

- Genital mycotic infections
- Urinary tract infections including urosepsis and pyelonephritis
- Diuretic effects including hypovolemia
- Hypotension episodes
- Hepatotoxicity
- Hypoglycemia
- Falls and fractures
- Malignancies

- Hypersensitivity reactions
- Acid-base disorders including DKA
- Renal failure events

AEs of special interest will be defined programmatically based on MedDRA system organ class and preferred terms which will be predefined by a blinded medical reviewer and will be specified in the Statistical Analysis Plan.

Event terms, signs, and symptoms will be documented in the listings. The number and percentage of subjects who have experienced treatment emergent adverse events (TEAEs) of special interest will be summarized for each treatment group by type of AE. A TEAE is an AE that started or worsened in severity at or after start of randomized treatment.

A case report form for adverse events that require amputation will be completed to capture the date and type of procedure, anatomic location, and causes. The number and percentage of subjects experienced any TEAE that requires amputation will be summarized for each treatment group by type of events. The incidence of lower extremity amputation per 100 patient years will also be summarized. Additional analyses will be specified in the statistical analysis plan to evaluate potential risks in subpopulations based on age, gender, or other baseline characteristics (if sample size allows).

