9.3.3. AE of Special Interest

AEs of special interest include UTI, pyelonephritis urosepsis, GMI, diuretic effects including hypovolemia, hypotension episodes, hypoglycemia, hepatotoxicity, cardiovascular events, fractures, malignancies, hypersensitivity reactions, acid-base disorders including diabetic ketoacidosis (DKA), rash, and renal failure events. These AEs of special interest, except for DKA, cardiovascular events and amputations, will be prospectively identified based on the MedDRA PTs in the AEs log by a medical expert prior to the data base lock and unblinding of the individual subject treatment assignment. The list of AEs of special interest will be confirmed in a peer review process. Cardiovascular events and DKA will be adjudicated and the confirmed MACE events (See Section 9.3.3.3), and confirmed or possible DKA events (See Section 9.3.3.5) will be summarized in the same AE of special interest table. The hypoglycemia events by severity, and amputations will be summarized separately.

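### The SAP keeps the protocol's amputation percentages but omits its lower-extremity rate per 100 patient-years, and narrows falls and fractures to fractures; its section on changes declares neither.

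*Combined protocol and SAP*

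**What the plan says.** **Amputations, protocol.** Section 9.6.4 plans two summaries. The first is a percentage: "The number and percentage of subjects experienced any TEAE that requires amputation will be summarized for each treatment group by type of events". The second is a rate: "The incidence of lower extremity amputation per 100 patient years will also be summarized".

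**Amputations, SAP.** Section 9.3.3.4 reads "Revascularization and amputation information is collected in a separate form. Frequency and percentage will be summarized for" four items: type of procedure, subjects with any amputation, the condition that led to it, and its location. Only procedures after the first double-blind dose count. No rate is mentioned. SAP 9.3.3 says of the special-interest events: "These AEs of special interest, except for DKA, cardiovascular events and amputations, will be prospectively identified based on the MedDRA PTs". It then adds: "The hypoglycemia events by severity, and amputations will be summarized separately".

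**Falls.** Protocol 9.6.4 has the special-interest category "Falls and fractures", and the synopsis pairs the two in the same way. The SAP 9.3.3 list runs "hepatotoxicity, cardiovascular events, fractures, malignancies, hypersensitivity reactions", with no falls. SAP 4.3 also names fractures only.

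**Which document governs.** Protocol 9.1 says that "a full analysis plan will be developed as a separate document and will become the final plan". SAP section 12, on changes from the protocol, covers the per-protocol base set, the model covariates, the primary analysis and the added exploratory objectives and endpoints. It is silent on amputation rates and falls. The SAP revision log for version 1.2 records, without detail, an update to the list of adverse events of interest.

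**The concern.** The protocol makes the SAP the final plan, so what the SAP leaves out will not be produced by anyone following it. Here that is one named safety rate and half of one named special-interest category.

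The rate matters because follow-up varies by design: protocol 9.2 assumes 1 to 3 years per subject with 6.5% annual withdrawal. A crude percentage mixes the event rate with length of follow-up, so the amputation figure cannot be set beside the per-100-patient-year figures that the SAP plans for adjudicated MACE and for preferred-term special-interest events.

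For falls, the special-interest list decides which events have their preferred terms chosen before database lock and unblinding, and which are counted as a group. Off the list, falls lose both. Removing protocol-listed safety output without a stated reason also invites questions about selective reporting that the sponsor could easily avoid.

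**Working it through.** The plan gives no figure to reproduce. The check is a comparison of the texts, followed by a small illustration.

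**1. Does another SAP section supply the amputation rate?**

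| SAP section | What it provides | Lower-extremity amputation rate? |
|---|---|---|
| 4.3 | Names amputations among events of interest; no statistic | No |
| 9 (opening list) | Lists incidence of amputations; no method or denominator | No |
| 9.3.3.1 | Rate per 100 patient-years for events identified by preferred term | No; 9.3.3 exempts amputations from that route |
| 9.3.3.3 | Rate per 100 patient-years for adjudicated MACE | No |
| 9.3.3.4 | Frequency and percentage | No |
| 6.2.6 | Patient-years: first dose to end of study, summed, divided by 365.25 | Denominator only |

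SAP 4.3 might lead someone to apply 9.3.3.1 to amputations. The exemption in 9.3.3 and the heading of 9.3.3.1 rule that out, and such a rate would not be specific to the lower extremity.

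**2. Where do falls appear?** Protocol synopsis and 9.6.4: paired with fractures. SAP 4.3 and 9.3.3: absent. A fall reported as a treatment-emergent event would still be counted by system organ class and preferred term under SAP 9.3.2.

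**3. How far does a crude percentage depend on follow-up?** The documents give no amputation rate, so the rates here are assumptions. Take a constant event rate h per year, a withdrawal hazard d = −ln(1 − 0.065) = 0.0672 per year (from protocol 9.2) and maximum follow-up T:

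- crude proportion = h/(h + d) × [1 − exp(−(h + d)T)]
- mean patient-years per subject = [1 − exp(−dT)]/d

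With h = 0.005 (0.5 per 100 patient-years), so h + d = 0.0722:

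- T = 1: 0.0693 × (1 − exp(−0.0722)) = 0.48%; mean patient-years 0.967; 0.48/0.967 gives 0.50 per 100 patient-years.
- T = 3: 0.0693 × (1 − exp(−0.2166)) = 1.35%; mean patient-years 2.717; 1.35/2.717 gives 0.50 per 100 patient-years.
- T uniform over 1 to 3 years: 0.93%; mean patient-years 1.862; 0.93/1.862 gives 0.50 per 100 patient-years.

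The percentage changes by a factor of 1.35/0.48 = 2.8 while the rate stays put. Over assumed rates of 0.2 to 1.0 per 100 patient-years, with T uniform over 1 to 3 years, the crude percentage runs from 0.37% to 1.84%.

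**4. Does this distort the comparison of arms?** Use the same rate of 0.5 in both arms and T uniform over 2 to 3 years. Annual withdrawal of 6.5% gives 1.14%; an assumed 13% gives 1.05%. Doubling withdrawal in one arm moves its percentage by 0.09 points, about 8% in relative terms (1.047/1.142 = 0.917). With equal withdrawal there is no such difference.

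**The case against.** Several points on the other side stand.

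- A reader might infer that the SAP swapped the rate for a percentage. It did not: the protocol already planned the percentage, and the SAP keeps it and leaves out the additional rate.
- A reader might infer that the change to the list was left wholly unrecorded. The version 1.2 log shows that the list was edited under version control. The entry names no event and no departure from the protocol, however, so it does not declare the removal of falls. The preferred-term list itself is not in these documents, so whether fall terms sit under fractures cannot be checked.
- A reader might infer that the protocol promised a rate for falls, or falls as a separate result. It promised neither. Falls and fractures form one category, and protocol 9.6.4 plans number and percentage by type; per-100-patient-year rates for these events are a SAP addition.
- A reader might infer that the crude percentage biases the treatment comparison. Arms are randomised concurrently and share a common end of treatment (protocol 6.12), so follow-up should be similar, and step 4 shows a small shift even under doubled withdrawal.
- The data are not lost. Procedure date and location are captured, and patient-years are defined.

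One argument mostly fails: that amputations are treated like other special-interest events because hypoglycemia and DKA also lack rates. Under SAP 9.3.3 hypoglycemia stays on the preferred-term list, and only its severity breakdown is separate. Adjudicated DKA goes into the same special-interest table, although its own section states no rate.

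**Conclusion.** Both omissions are real. Followed as written, the SAP does not produce the lower-extremity amputation rate that protocol 9.6.4 calls for, and it does not treat falls as part of a special-interest category. Section 12 declares neither departure.

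The weight is modest. These are descriptive safety summaries; no hypothesis test, error rate, sample size or primary result depends on them. The amputation percentage has no time base under variable follow-up, so it is not comparable with the rates planned for MACE and the preferred-term events. That is a matter of interpretation and completeness, not of material bias between arms, unless withdrawal differs by arm.

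The textual conclusion needs no assumptions. The sizes in the illustration rest on constant event and withdrawal rates, on assumed amputation rates of 0.2 to 1.0 per 100 patient-years, and on the follow-up and withdrawal figures in protocol 9.2. It is worth correcting because the commitments are explicit and the correction is nearly free.

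**What to change.** 1. In SAP 9.3.3.4, add by treatment arm the number of subjects with a lower-extremity amputation and the incidence per 100 patient-years, using the section 6.2.6 denominator. State whether the numerator counts subjects or events. SAP 9.3.3.1 counts events, and the 6.2.6 denominator runs to end of study whether or not an event has occurred, so it matches an event count directly; a count of subjects should be labelled as such.
2. In SAP 4.3 and 9.3.3, restore falls beside fractures and include fall terms in the preferred-term selection made before lock. If the removal was intended, declare and justify it in section 12 instead.

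Cost: a table row or two and a term list. No new data collection is needed, since amputation date and location are already recorded and patient-years are already defined.
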